7.7.3. Clinical Laboratory Data

Clinical laboratory parameters will be expressed in Standard International (SI) units. Laboratory data collected and recorded as below the lower limit of quantitation (LLOQ) will be set to the LLOQ for calculation of summary statistics. Key laboratory parameters will be graded according to NCI CTCAE v5.0.

Clinical laboratory data by visit in summary tables will use data from central laboratory.

eDISH plots and the summary tables and listings for abnormality for clinical laboratory data will be analyzed in two ways; one using only central laboratory data and one using both central and local laboratory data by the following rules;

- Central laboratory data at both scheduled and unscheduled visits will be used.
- If central laboratory data at a visit is missing, local laboratory data will be used.
- If a patient has both local and central laboratory data at the same visit, the central data will be used.

Shift tables will be generated to summarize shifts from baseline category to the worst post-baseline category with directionality specified (e.g. hyper and hypo).

Clinical laboratory tests with normal ranges will be classified as Low, Normal, and High. For these tests, abnormal values will be flagged in the listings with H when the value is higher than the upper limit of the reference ranges and with L when the value is lower than the lower limit of the reference ranges.

For hematology and chemistry labs, summary tables of potentially clinically significant abnormalities may also be provided.

- All laboratory data will be presented in data listings. The listing of the clinical laboratory data will display both local and central laboratory data. Out of range laboratory results will be identified in listings.

LFTs: A listing will be generated for all patients with abnormal liver function tests as defined by alanine aminotransferase (ALT)>3xULN, aspartate aminotransferase (AST)>3xULN or total bilirubin >2x ULN at any visit.

A tabular summary for LFTs will be generated to summarize the number and associated percentage of patients in each of the categories at any post-baseline visit:

- ALT: Within normal limit (WNL), $1 < \text{ALT} \leq 3$, $3 < \text{ALT} \leq 5$, $5 < \text{ALT} \leq 10$, $10 < \text{ALT} \leq 20$, $\text{ALT} > 20 \times \text{ULN}$
- AST: WNL, $1 < \text{AST} \leq 3$, $3 < \text{AST} \leq 5$, $5 < \text{AST} \leq 10$, $10 < \text{AST} \leq 20$, $\text{AST} > 20 \times \text{ULN}$
- ALT or AST: WNL, $1 < \text{ALT or AST} \leq 3$, $3 < \text{ALT or AST} \leq 5$, $5 < \text{ALT or AST} \leq 10$, $10 < \text{ALT or AST} \leq 20$, $\text{ALT or AST} > 20 \times \text{ULN}$
- ALP: WNL, $1 < \text{ALP} \leq 1.5 \times \text{ULN}$, $\text{ALP} > 1.5 \times \text{ULN}$
- Total Bilirubin: WNL, $1 < \text{Total Bilirubin} \leq 1.5$, $1.5 < \text{Total Bilirubin} \leq 2$, $2 < \text{Total Bilirubin} \leq 3$, $3 < \text{Total Bilirubin} \leq 5$ and $\text{Total Bilirubin} > 5 \times \text{ULN}$

eDISH plots of peak bilirubin at any time versus peak ALT or AST at any time will also be presented.

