#### **5.2.3.1. Liver Function Test Criteria for Withholding, Monitoring and Stopping Lumasiran Dosing**

1. For patients who weigh <20 kg, liver function test (LFT) results (see [Table 10](#)) are to be obtained within 7 days prior to dosing and results are to be reviewed prior to each dose of lumasiran. During periods of time when the COVID-19 pandemic impedes the ability of patients to travel to the study site or healthcare professionals to go to patients' homes and LFT assessments are not feasible within 7 days prior to the dose, LFT test results up to 6 weeks prior to the planned monthly dose or up to 4 months prior to the planned quarterly dose may be reviewed to determine whether the dose can be administered.

For patients who weigh  $\geq$ 20 kg, LFT results may be reviewed up to 4 months prior to the planned quarterly dose to determine whether the dose can be administered.

2. Consult the Laboratory Manual for the blood draw priority list based on patient weight. Central laboratory results are preferable. If not available, local laboratory results may be used; however, if a local assessment is drawn, a serum chemistry sample must also be drawn for analysis at the central laboratory.
3. For any ALT or AST elevation  $>3\times$  ULN, central laboratory results should be used to guide subsequent monitoring as detailed in [Table 8](#).

4. For any ALT or AST elevation  $>3 \times$  ULN:
  - a. If local laboratory results are obtained, confirm using central laboratory, as soon as possible, ideally within 2 to 3 days, but no later than 7 days.
  - b. If an alternative cause is found, provide appropriate care.
  - c. If an alternative cause is not found, perform assessments per [Table 8](#) and [Table 11](#).
5. For any ALT or AST elevation  $>3 \times$  ULN without alternative cause that is accompanied by clinical symptoms consistent with liver injury (eg, nausea, right upper quadrant abdominal pain, jaundice) or elevated bilirubin to  $\geq 2 \times$  ULN or international normalized ratio (INR)  $\geq 1.5$ , permanently discontinue dosing.
6. For confirmed ALT or AST elevations  $>3 \times$  ULN without alternative cause and not accompanied by symptoms or elevated bilirubin  $\geq 2 \times$  ULN or INR  $\geq 1.5$ , see [Table 8](#):

**Table 8: Monitoring and Dosing Rules for Asymptomatic Patients with Confirmed Isolated Elevations of ALT and/or AST  $>3\times$  ULN, with No Alternative Cause Identified**

Transaminase Level	Action

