### **6.5.5. Clinical Laboratory Assessments**

The following clinical laboratory tests will be evaluated by a central laboratory, except in cases where it is not feasible to perform all tests centrally due to blood draw volume limits, ie, in infants and very young patients, hematology, and biochemistry panels may be performed locally, with central laboratory confirmation of any abnormalities. Specific instructions for transaminase elevations are provided in Section [5.2.3.1](#). For any other unexplained clinically relevant abnormal laboratory test occurring after study drug administration, the test should be repeated and followed up at the discretion of the Investigator, or as per DMC advice, until it has returned to the normal range or stabilized, and/or a diagnosis is made to adequately explain the abnormality. Additional safety laboratories and assessments as indicated by the clinical situation

may be requested. Clinical laboratory assessments are listed in [Table 10](#) and will be assessed as specified in the Schedules of Assessment (see [Table 1](#), [Table 2](#), [Table 3](#), and [Table 4](#)).

While local laboratory results may be used for urgent clinical and dosing decisions, on the day of the visit assessments, all laboratory assessments specified in [Table 10](#) which are performed at a local laboratory should also be sent in parallel to the central laboratory. Central laboratory results (once available) should be used for subsequent clinical and dosing decisions in the case of discrepant local and central laboratory results on samples drawn on the same day.

For any safety event or laboratory abnormality, additional laboratory assessments, imaging, and consultation may be performed for clinical evaluation and/or in consultation with the Medical Monitor; results may be collected and should be included in the clinical database.

Consult the Laboratory Manual for the blood draw priority list based on patient weight (see Section [6.5.5.4](#)).

Clinical laboratory assessments may be collected at the clinical site or at a location other than the clinical study center by a trained healthcare professional.

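### In the central-plus-local liver summaries, a later central value filed under the same visit can displace a higher local one, so the plotted peak need not be the peak

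*SAP*

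**What the plan says.** SAP 7.7.3 plans two versions of the eDISH plots and of the abnormality tables and listings: "one using only central laboratory data and one using both central and local laboratory data by the following rules". Central data from scheduled and unscheduled visits are always used. A local result enters by one route: "If central laboratory data at a visit is missing, local laboratory data will be used". Where both exist, "If a patient has both local and central laboratory data at the same visit, the central data will be used". No exception is made for ALT, AST or bilirubin.

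The outputs fed by this rule are described as worst-value summaries. For the plot, "eDISH plots of peak bilirubin at any time versus peak ALT or AST at any time will also be presented". The liver table counts the "number and associated percentage of patients in each of the categories at any post-baseline visit". Shift tables run from baseline to the worst post-baseline category. SAP 5.6 assigns data to the visit recorded in the eCRF, even when the assessment falls outside its window.

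On the protocol side, section 6.5.5 begins one sentence with "While local laboratory results may be used for urgent clinical and dosing decisions" and then gives central results precedence for later decisions when local and central results from samples drawn on the same day disagree. Section 5.2.3.1 (item 4a) says of a local ALT or AST above 3×ULN: "confirm using central laboratory, as soon as possible, ideally within 2 to 3 days, but no later than 7 days".

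**The concern.** The two documents define precedence on different units. The protocol compares two samples from one day. The SAP compares two results under one visit label, which may be several days apart. A transaminase peak can fall within those days, so a later central value may be lower because the child has improved, not because the local assay was wrong.

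The central-plus-local version is the only summary that could show a peak seen by a local laboratory alone. Protocol 1.5 names liver function test abnormalities as one of two important potential risks, and 6.5.6.1 makes ALT or AST above 3×ULN an adverse event of clinical interest. A local value that prompted a work-up could therefore be missing from both versions of the eDISH plot and the category table.

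The loss could also be selective. Protocol 6.5.5 lets infants and very young patients have panels run locally because of blood-volume limits, with central confirmation of abnormalities. Under that allowance a normal local value has no central partner and is kept; an abnormal one attracts a central repeat and may be replaced.

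**Working it through.** The plan states no figure on this point, so there is nothing to reproduce. The check applies the SAP rule to each way in which the samples might be drawn and filed.

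**Step 1. Rule.** For each visit label, selected value = central if present, otherwise local. Plotted peak = maximum of the selected values over visits. True recorded peak = maximum of all values.

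**Step 2. Three filing cases for an elevated local value.**
- A: a central sample was drawn the same day. The local value is dropped. This agrees with the protocol's hierarchy, and the two values should differ mainly by between-laboratory variation.
- B: there is no same-day central sample, and the confirmation is filed as an unscheduled visit. Central is missing at the original visit, so the local value is kept and the peak is right.
- C: there is no same-day central sample, and the confirmation is filed under the original visit. Central is present for that label, so the local value is dropped although it was drawn on another day.

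The documents do not say whether a confirmation is filed as in B or as in C.

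**Step 3. Illustration (assumed values).** Local ALT is 5.5×ULN; central ALT six days later is 2.8×ULN; all other visits are lower.
- Case B: peak = max(5.5, 2.8) = 5.5, in the >5 to 10 row.
- Case C: peak = 2.8, in the >1 to 3 row.
- Central-only version: 2.8 in both cases.

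One such child changes a category rate by 1/20 = 5 percentage points at the planned enrolment, or 1/16 = 6.25 points at the interim analysis of the first 16 patients.

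**Step 4. Same-day pairs (case A).** Suppose both laboratories measure the same underlying ALT with independent log-normal error and no systematic difference. Let p be the chance that one result exceeds 3×ULN. Then P(local >3, central ≤3) = p(1 − p). This is also the extra chance of being counted above 3×ULN if the higher of the two is always taken. A simulation with assumed CVs of 5%, 10% and 20% gave:
- underlying ALT 2.8×ULN: 0.077, 0.185, 0.231
- underlying ALT 3.0×ULN: 0.251, 0.250, 0.250 (formula: 0.5 × 0.5 = 0.25)
- underlying ALT 3.2×ULN: 0.089, 0.191, 0.233

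The local value was the higher of the pair about half the time. Near the cut-off, therefore, taking the maximum of same-day pairs adds cases through assay noise alone. Case C is different: the two samples are from different days, and the earlier value may be a real peak.

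**The case against.** The strongest reply is that central precedence is the protocol's own hierarchy. Section 5.2.3.1 has central results guide monitoring above 3×ULN, the dosing rules in Table 8 apply to confirmed elevations, and 6.5.5.3 starts the extended hepatic work-up from central results. SAP section 8 records this data handling as a deliberate alignment with Amendment 2. For same-day pairs that reply stands, and Step 4 shows that always taking the higher value has a cost. It does not cover samples drawn on different days, where the protocol's stated precedence for discrepant results does not reach.

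It is also fair to say that case C is assumed. It needs a missing same-day central sample, although 5.2.3.1 (item 2) requires one with each local draw, and it needs a particular filing choice. The point is that the SAP rule leaves this open.

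Two stronger readings are tempting.
- A reader might infer that the combined version almost duplicates the central-only one, because central samples accompany local draws. The blood-volume exception in 6.5.5 allows local-only panels, and SAP 5.5 expects missing blood results for the same reason. Those local values do enter, so the share displaced is unknown.
- A reader might infer that a liver event would go unreported. It would not: "The listing of the clinical laboratory data will display both local and central laboratory data", with out-of-range results identified. Events of clinical interest have their own eCRF and 24-hour notification, and SAP 7.7.1 tabulates hepatic adverse events and those leading to treatment interruption. The abnormality listings, however, follow the same selection rule as the plot, so among the laboratory outputs only the full listing is sure to show the displaced value.

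**Conclusion.** The point holds in a limited form. As written, the SAP rule allows a later central value to displace an earlier, higher local ALT, AST or bilirubin under the same visit label, which is broader than the protocol's same-day precedence. The plotted peak is then the peak of the selected values, not of all recorded values. The consequence is confined to the central-plus-local eDISH plot, abnormality tables and abnormality listings; no efficacy result is touched.

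The size is one category shift per affected child: 5 percentage points in 20. That figure and the 5.5 to 2.8×ULN example are illustrations. The frequency depends on how confirmations are filed and how often same-day central samples are missing, and the documents give neither. This is worth correcting because it is cheap and concerns a named risk, but it is a minor point.

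**What to change.** In SAP 7.7.3, for the central-plus-local version only:
- Apply central precedence only when the local and central samples were drawn on the same date.
- Otherwise include every local value when taking the worst value for the eDISH plots, the liver category tables and the shift-to-worst tables, expressing each as a multiple of the ULN of the laboratory that measured it.
- For same-day discordant pairs, choose one rule in advance: keep central precedence and say so on the plot, or take the higher multiple of ULN and accept some upward noise near the cut-offs.

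Leave the central-only version unchanged; it remains the check on any spurious local result.

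The cost is one reworded rule and a small programming change. It assumes that draw dates and local reference ranges are held in the database. No additional sample or visit is needed.

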7.7.4. Vital Signs

A summary table of potentially clinically significant shifts in vital signs may be generated.

A summary table of descriptive statistics of modified z-scores of patient height, weight, and BMI by visits will be generated. A tabular summary of the proportion of patients with z-scores at various cut-points (i.e. $\geq +/- 2$ SD) will also be generated.

A by-patient listing of vital sign data will be generated. Per patient plots of z-scores over time may also be generated.

7.7.5. Physical Examinations

Full physical examinations and symptom-directed physical examinations will be conducted throughout the study. Clinically significant abnormalities observed during the physical examination are recorded on the medical history or AE eCRF as appropriate.

A separate listing per patient will be generated to display the date and time of the physical exam.

7.7.6. Electrocardiogram

Rhythm from single Electrocardiogram (ECG) parameter will be collected. The number and percentage of patients with normal, abnormal, clinically significant abnormal results, and specified abnormalities at baseline and each timepoint will be summarized.

A listing of all ECG data will be provided.

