### **6.5.4. Electrocardiogram**

Single 12-lead ECGs will be obtained predose, when applicable, at the timepoints specified in the Schedules of Assessment (see [Table 1](#), [Table 2](#), [Table 3](#), and [Table 4](#)). During periods of time when the COVID-19 pandemic impedes the ability of patients to travel to the study site, ECG assessments may be completed up to 3 months after the intended timepoint for assessments scheduled prior to Month 12, and up to 9 months after the intended timepoint for visits at Month 12 and later. 12-lead ECGs will be locally read.

When ECG and blood sample collection occur at the same time, ECGs should be performed before blood samples are drawn and when the patient is calm.

The Investigator or qualified designee will review all ECGs to assess whether the results have changed since the Baseline visit and to determine the clinical significance of the results. These assessments will be recorded on the eCRF. Additional ECGs may be collected at the discretion of the Investigator, or as per DMC advice. Recordings will be archived according to the Study Manual.

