### **7.2.8. Safety Analyses**

The main parameter is the frequency of treatment-emergent AEs (hereafter referred to simply as AEs). Safety parameters also include vital signs, ECGs, clinical laboratory assessments and physical exams. Extent of exposure will be summarized overall.

Prior and concomitant medications will be classified according to the World Health Organization (WHO) Drug Dictionary. Results will be tabulated by Anatomical Therapeutic Chemical (ATC) Classification System and Preferred Term (PT).

AEs will be classified according to the Medical Dictionary for Regulatory Activities (MedDRA) overall. AEs, SAEs, related AEs, and AEs leading to discontinuation will be summarized by System Organ Class (SOC) and PT for each treatment arm. By-patient listings will be provided for deaths, SAEs, and events leading to discontinuation of treatment.

Descriptive statistics will be provided for clinical laboratory data, ECG, and vital signs data. Laboratory shift tables from baseline to worst values will be presented.

Other safety summaries will be presented as appropriate. Further details will be specified in the SAP.

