5.6. Visit Windows

For tabular and graphical summaries, all data will be tabulated and analyzed per the evaluation visit as recorded on the electronic case report forms (eCRF) even if the assessment is outside of window.

Unless otherwise specified, data collected at an unscheduled visit will be included in by-patient listings and/or spaghetti plot figures, but no assignment of the scheduled visit will be made for the purposes of summary tabulations. However, unscheduled study visits will be used in the calculation of baseline values if prior to first dosing and for any categorical shift tables (e.g. shift from baseline to worst post-baseline value).

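### The planned ECG table gives counts per timepoint only, so on its own it does not in general show new or worse abnormalities, and post-dose ECGs from unscheduled visits enter no ECG table.

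*SAP*

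**What the plan says.** - **Planned ECG output.** SAP 7.7.6 specifies one table: "The number and percentage of patients with normal, abnormal, clinically significant abnormal results, and specified abnormalities at baseline and each timepoint will be summarized". It then adds: "A listing of all ECG data will be provided". It names no shift, worst post-baseline or new-onset summary.
- **Unscheduled visits.** Under SAP 5.6, data from an unscheduled visit go to listings and spaghetti plots, and "no assignment of the scheduled visit will be made for the purposes of summary tabulations". Two uses are excepted: "unscheduled study visits will be used in the calculation of baseline values if prior to first dosing and for any categorical shift tables".
- **Extra ECGs.** Protocol 6.5.4 provides: "Additional ECGs may be collected at the discretion of the Investigator, or as per DMC advice".
- **Change since baseline.** The same section has the Investigator or a qualified designee "review all ECGs to assess whether the results have changed since the Baseline visit" and judge clinical significance, with both assessments entered on the eCRF. SAP 7.7.6 names no summary of the change assessment.
- **Laboratory data, for comparison.** SAP 7.7.3 says: "Shift tables will be generated to summarize shifts from baseline category to the worst post-baseline category". Protocol 7.2.8 says: "Laboratory shift tables from baseline to worst values will be presented". For ECG, Protocol 7.2.8 promises descriptive statistics.

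**The concern.** The trial has a single arm, so each child's own baseline is the only comparator for ECG safety within the study. Separate counts at baseline and at each visit discard that pairing. If the same number of children is abnormal before and after dosing, the table cannot tell persistent abnormality from one child recovering while another becomes abnormal. The same applies to worsening from an abnormality that is not clinically significant to one that is.

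Extra ECGs are plausibly done because something prompted them. If they fall at an unscheduled visit after dosing, the ECG table leaves them out. The clinical study report would then contain no pre-specified count, denominator or handling rule for new or worse ECG abnormality. A reader would have to build one by hand from the listing.

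**Working it through.** The plan states no figure on this point that could be reproduced. The sample size of 20 rests on feasibility (SAP 5.1), and the documents give no ECG abnormality rates. The check has two parts.

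**1. What two separate counts can identify**

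Inputs: n = 20 children (SAP 5.1), all assumed to have an ECG at baseline and at the visit. Let b be the number abnormal at baseline and f the number abnormal at the visit. The values of b and f below are assumptions.

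Let x be the children normal at baseline and abnormal at the visit, and y those abnormal at both. Then x + y = f, with y between 0 and b, and x between 0 and n − b. Therefore

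max(0, f − b) ≤ x ≤ min(f, n − b).

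| b | f | Lower bound | Upper bound | At risk (n − b) |
|---|---|---|---|---|
| 0 | 1 | max(0, 1) = 1 | min(1, 20) = 1 | 20 |
| 1 | 1 | max(0, 0) = 0 | min(1, 19) = 1 | 19 |
| 3 | 3 | max(0, 0) = 0 | min(3, 17) = 3 | 17 |
| 3 | 4 | max(0, 1) = 1 | min(4, 17) = 4 | 17 |

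With nobody abnormal at baseline, the table gives the new-onset count at that visit exactly. With one or more abnormal at baseline, it generally gives only a range. The same bounds hold for any single category, such as clinically significant abnormality, if b and f are the counts in that category.

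**2. Where a post-dose ECG from an unscheduled visit goes**

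- SAP 5.6 does not assign it to a scheduled visit, so it is absent from the per-timepoint table of SAP 7.7.6.
- The baseline exception in SAP 5.6 does not apply, because the ECG is after the first dose.
- The shift-table exception would apply, but SAP 7.7.6 plans no shift table.
- It therefore appears in the ECG listing and in no ECG table.

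The gap is specific to ECG. The SAP plans shift tables for laboratory data (7.7.3), eGFR including the overall worst value (7.3), nephrocalcinosis grade and Vineland adaptive levels (both 7.4). It summarises anti-drug antibodies at any post-baseline visit (7.8).

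**The case against.** The strongest reply is that nothing is lost and the plan is proportionate. Much of this stands.

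- **Listings.** All ECG data are listed (SAP 7.7.6), as are all CRF data (SAP 5.2), which covers the Investigator's change assessment. With about 20 children, new onset can be read off directly. A reader might infer that new-onset abnormality cannot be derived at all; that is true only of the summary table.
- **Adverse events.** Protocol 6.5.6.2 has ECG changes relevant to patient safety documented as adverse events. Treatment-emergent events are tabulated by System Organ Class and Preferred Term (SAP 7.7 and 7.7.1). A reader might infer that an ECG done because of a concern reaches no table. A relevant change on it does reach the adverse event tables, and an extra ECG recorded under a scheduled visit is not excluded by SAP 5.6. What remains outside every table is an abnormality on an unscheduled-visit ECG that is not judged reportable.
- **Children abnormal at baseline.** It is tempting to say that such a child is counted as abnormal at every later timepoint. The table counts each child by that timepoint's reading, so a child who normalises is counted as normal.
- **Specified abnormalities.** The table also reports these by timepoint. One that no child had at baseline is visibly new when it appears. This is the b = 0 case above and does not help where the baseline count is above zero.
- **Consistency and proportion.** Protocol 7.2.8 names shift tables for laboratory data only, and the SAP follows it. Protocol 1.5 names injection site reactions and liver function abnormalities as the important potential risks. The Amendment 2 summary of changes reports no QTc-prolonging properties. So there is no contradiction between the documents. Protocol 7.2.8 also leaves further safety summaries to the SAP, so the addition is open to the sponsor.

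**Conclusion.** The point holds as a minor reporting gap. The planned ECG table does not in general identify new or worse abnormality once any child is abnormal at baseline, and post-dose ECGs from unscheduled visits enter no ECG table. No data are lost and the primary endpoint is untouched.

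Under the assumed counts of 3 abnormal at baseline and 3 at a visit among 20 children, the uncertainty is 0 to 3 new cases among 17 at risk at that visit. This rests on complete ECGs at both times and on counts chosen for illustration. If no child is abnormal at baseline, the per-visit uncertainty vanishes, although the omission of unscheduled-visit ECGs remains.

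A reader might carry the illustration across all seven scheduled post-baseline ECGs (Months 3, 6, 12, 24, 36, 48 and 60). With 3 abnormal each time there are 7 × 3 = 21 abnormal readings, enough for all 17 baseline-normal children to be abnormal at some visit. That is a logical bound, not a plausible size. It leaves at most 21 − 17 = 4 abnormal readings for the three children abnormal at baseline, so they would have to be normal at most visits while abnormality rotates through every other child. Nothing in the documents suggests such a pattern.

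**What to change.** Add to SAP 7.7.6:

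1. A shift table from baseline ECG category to worst post-baseline category in the Safety Analysis Set. The categories are normal, abnormal not clinically significant, and abnormal clinically significant. State that ECGs from unscheduled visits are included, as SAP 5.6 already provides for categorical shift tables, and show the number of children in each baseline category as denominator.
2. The number of children with a change since baseline as recorded by the Investigator on the eCRF.

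Keep the per-timepoint table and the listing. The cost is one table and one added count, both from data already collected, with no new procedures and no effect on any endpoint.
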